9.5. Adjustment for Multiplicity

No adjustments for multiplicity will be made.

10. IMAGING OUTCOMES

The change from baseline in the outcome will be compared between the treatment groups using the MMRM or ANCOVA model described in section 9.3.

The pooled analysis and analysis by arm will be performed with data for the composite regions and for the individual exploratory regions collected for points up to and including the 6-month time point. This analysis will be considered the primary analysis.

A separate pooled analysis and analysis by arm will also be performed with data for the composite regions and for the individual exploratory regions at time points up to and including the 12-month time point.

10.1. [¹¹C] UCB-J PET Distribution Volume Ratio (DVR)

For ¹¹C-UCB-J, the primary imaging outcome measure is *DVR* as produced by the Simplified Reference Tissue Model (SRTM2) using dynamic scan data from 0 to 60 min and the whole cerebellum as a reference region. For *DVR*, a composite region will be determined, including: prefrontal, lateral temporal, posterior cingulate/precuneus, anterior cingulate, lateral parietal, medial temporal, and lateral occipital regions. For the ¹¹C-UCB-J DVR outcome composite region the primary model will be analyzed without reference to age and ApoE4 status, however additional models will be run that include age and ApoE4 status as sensitivity analyses. Analyses will also be conducted to assess the relationship of age and ApoE4 status with the dependent DVR variable and to determine if there is any imbalance on these variables between the treatment groups.

Regional analyses will first focus on the hippocampus since the recent cross-sectional study has shown this to be the region of largest group differences in synaptic density when comparing a group of participants with AD to healthy participants.

Individual exploratory regions include:

- Hippocampus
- Entorhinal cortex
- Parahippocampal cortex
- Amygdala
- Fusiform gyrus

- Lingual gyrus
- Inferior/middle temporal cortex
- Anterior cingulum
- Posterior cingulum
- Precuneus
- Prefrontal cortex
- Superior temporal cortex
- Lateral parietal cortex
- Lateral occipital cortex
- Pericentral cortex
- Medial occipital cortex

10.2. [¹⁸F]FDG PET SUV ratio (SUVR)

For ¹⁸F-FDG, the primary imaging outcome measure is the *SUVR* from 60-90 min post injection using whole cerebellum as a reference region. For *SUVR*, a composite region will be determined, including: prefrontal, lateral temporal, posterior cingulate/precuneus, anterior cingulate, lateral parietal, medial temporal, and lateral occipital regions.

Individual exploratory regions include:

- Hippocampus
- Entorhinal cortex
- Parahippocampal cortex
- Amygdala
- Fusiform gyrus
- Lingual gyrus
- Inferior/middle temporal cortex
- Anterior cingulum
- Posterior cingulum
- Precuneus
- Prefrontal cortex
- Superior temporal cortex
- Lateral parietal cortex
- Lateral occipital cortex
- Pericentral cortex
- Medial occipital cortex

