### **17.5 Power Analysis**

Computation of sample size in this within-participant design was based on estimates of the magnitude of reductions in synaptic density from post-mortem AD data of 25-45%. It is assumed that, on average, there is 30% loss of synapses in this population, and that CT1812 will restore one third of those synapses, with no change in synaptic density in the placebo group. Based on the excellent test/retest reliability of  $^{11}\text{C}$ -UCB-J, it is conservatively assumed that there will be 10% variability in baseline and post-treatment  $^{11}\text{C}$ -UCB-J binding potential non-displaceable ( $\text{BP}_{\text{ND}}$ ) measurements.

Power is first computed by assessing whether the change in synaptic density would be larger in the treated group than the placebo group. For group sizes of 7 per group, we have ~68% power for comparison of the combined treatment of N=14 CT1812 vs. 7 placebo subjects ( $\alpha = 0.05$ , 1-tailed test). Higher power is present in the one-sample test of the treatment group, i.e., does synaptic density increase following CT1812 treatment. In that case, a group size of 7 CT1812 patients yields 80% power to detect an increase in synaptic density. Power for detecting changes in  $^{18}\text{F}$ -FDG is likely to be lower since the magnitude of change in the SV2A signal in AD will be larger than that of  $^{18}\text{F}$ -FDG (20%)(Landau et al, 2012).

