4.5. Sample Size

Computation of sample size in this within-participant design was based on estimates of the magnitude of reductions in synaptic density from post-mortem AD data of 25-45%. It

was assumed that, on average, there is 30% loss of synapses in this population, and that CT1812 would restore one third of those synapses, with no change in synaptic density in the placebo group. Based on the excellent test/retest reliability of ^{11}C UCB J, it was conservatively assumed 10% variability in baseline and post-treatment ^{11}C UCB J binding potential non-displaceable (BPND) measurements. Power was first computed by assessing whether the change in synaptic density would be larger in the treated group than the placebo group.

For group sizes of 7 per group, one has ~68% power for comparison of the combined treatment of N=14 CT1812 vs. 7 placebo subjects ($\alpha = 0.05$, 1-tailed test). Higher power was present in the one-sample test of the treatment group, i.e., did synaptic density increase following CT1812 treatment. In that case, a group size of 7 CT1812 patients yields 80% power to detect an increase in synaptic density. Power for detecting changes in 18F FDG is likely to be lower since the magnitude of change in the SV2A signal in AD will be larger than that of 18F FDG (20%).

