9.3. Efficacy Analysis

The change from baseline in the composite scores and clinical outcomes will be analyzed using a mixed effects model including fixed effects for treatment group (i.e. 300 mg active, 100 mg active, placebo), visit and treatment by visit interaction. In addition, the subject's baseline score will be included as a covariate. For each time point up to and

including 6-months, the treatment differences between 300 mg active and placebo, and 100 mg active and placebo will be estimated from the model. In addition, the low and high CT1812 dosed groups will be pooled and compared with the placebo group. This analysis will be considered the primary analysis.

A separate pooled analysis and analysis by arm will also be performed for time points up to and including the 12-month time point.

Additionally, p-values and corresponding two-sided confidence intervals will be provided. The LS Mean Change from Baseline in ADAS-Cog total scores with 95% CI will be presented graphically by treatment group over time.

In the event that a scale or parameter only has a single post-baseline timepoint, an ANCOVA model will be run in place of the MMRM model without the visit and visit by treatment interaction terms. The ANCOVA model will include a fixed effect for treatment group, and the subject's outcome at baseline as a covariate. For parameters for which there are multiple post-baseline timepoints, ANCOVA models such as that just described above may also be run in addition to the MMRM model at various timepoints.

The change from baseline in the ADAS-Cog (sub) scale total score, total time (in seconds) taken to complete both Trail A and Trail B in the NTB, ADCS-ADL total score, MMSE, CDR-SB, and composite scores will be analysed using the MMRM model described above.

To compare 300 mg active vs placebo and 100 mg vs placebo statistically, observed values for ADCS-CGIC will be analyzed using the MMRM model described earlier without the baseline term. Additionally, frequencies and percentages in the ADCS-CGIC will be summarized by visit. Cochran-Mantel-Haenszel mean score statistics, using rank scores will be used to assess the difference in ADCS-CGIC responses at each visit between the CT1812 dose levels and placebo.

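### For the primary imaging endpoint, the SAP labels the pooled and by-arm analyses up to Month 6 jointly as primary and does not say which contrast or visit leads

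*SAP*

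**What the plan says.** Safety is the primary objective. The SV2A PET change is a secondary endpoint, but Protocol 6.2.2 and SAP 4.6 both call it the primary imaging endpoint.

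- **SAP 10:** "The pooled analysis and analysis by arm will be performed with data for the composite regions and for the individual exploratory regions", for time points up to and including Month 6. The next sentence gives this the primary label. A separate analysis through Month 12 follows, outside the label.
- **SAP 9.3** (the model that section 10 borrows): at each time point up to Month 6, each dose is compared with placebo, and the pooled doses are compared with placebo. Then: "This analysis will be considered the primary analysis". P-values and two-sided confidence intervals are reported.
- **SAP 10.1:** the outcome is DVR. The composite region has a primary model; the 16 single regions are listed as exploratory.
- **SAP 9.5:** "No adjustments for multiplicity will be made".
- **SAP 4.5 and Protocol 17.5:** "For group sizes of 7 per group, one has ~68% power for comparison of the combined treatment of N=14 CT1812 vs. 7 placebo subjects", at alpha 0.05, one-tailed. A second figure is for a one-sample test: "a group size of 7 CT1812 patients yields 80% power to detect an increase in synaptic density".
- **Protocol 17.4:** the primary analysis uses post-baseline visits up to Month 6, and the model may be run again through Month 12.
- **Protocol 10.2.8 and 10.2.12:** post-baseline UCB-J scans fall on Day 85 and Day 169 within the primary study.

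**The concern.** For composite DVR, the text under the primary label yields three contrasts at two visits, that is, six estimates with six p-values. Neither document says which one answers the imaging question. The sample-size text was built around one between-group contrast, pooled versus placebo, and names no visit for it.

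With seven participants per arm, the six results can easily point in different directions. If the lead comparison is chosen after unblinding, that choice can decide whether the SV2A result, which is the question in the study's title, reads as positive. The by-arm contrasts also share the primary label although they are less well powered than the contrast used for planning.

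**Working it through.** **1. Reproduce the stated power (pooled, 14 versus 7).**

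Inputs from Protocol 17.5 and SAP 4.5:
- Effect: "there is 30% loss of synapses in this population, and that CT1812 will restore one third of those synapses". One third of 30 is 10 points of the normal level. Relative to a patient baseline of 70 this is 10/70 = 14.29%. Placebo change is 0.
- Variability: 10% per scan. If the errors of the two scans are independent (an assumption; no correlation is given), the SD of change is 10% × √2 = 14.14%.
- Alpha 0.05, one-tailed.

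Standard error = 14.14 × √(1/14 + 1/7) = 6.547. Noncentrality = 14.29 / 6.547 = 2.182, on 19 degrees of freedom.
- One-sided, critical t 1.729: power **67.7%**, which agrees with the stated 68%.
- Two-sided, critical t 2.093: power **54.4%**.

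**2. The by-arm contrasts on the same inputs (7 versus 7).**

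Standard error = 14.14 × √(2/7) = 7.559. Noncentrality = 14.29 / 7.559 = 1.890, on 12 degrees of freedom.
- One-sided, critical t 1.782: power about **55%**.
- Two-sided, critical t 2.179: power about **41%**.

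**3. Count what lies under the label for DVR up to Month 6.**

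- Composite region only: 3 contrasts × 2 visits = 6 tests.
- Section 10 read literally: (1 composite + 16 exploratory regions) × 3 × 2 = 102 tests. Because section 10.1 points to the composite, the figures below use the composite only.

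**4. Chance of at least one nominal two-sided p<0.05 under no effect, composite DVR.**

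This was simulated with 7/7/7 participants, normal data, and t tests on the pooled within-arm variance (18 degrees of freedom). The three contrasts share the placebo arm, and the pooled contrast reuses both active arms, so they are strongly correlated.

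| Tests counted | Between-visit correlation (assumed) | Chance of at least one p<0.05 |
|---|---|---|
| 3 contrasts, 1 visit | not applicable | about 9% |
| 3 contrasts, 2 visits | 0.8 | about 14-15% |
| 3 contrasts, 2 visits | 0.5 | about 17% |
| 3 contrasts, 2 visits | 0.3 | about 18% |

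The documents give no between-visit correlation, so the range is an assumption. The simulation uses simple t tests and not the baseline-adjusted mixed model, so the figures show the order of magnitude.

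**The case against.** The best defence is that the primary label marks a data window. Protocol 17.4 uses the term for data up to Month 6, and SAP 9.3 and 10 follow that pattern, with a separate run to Month 12. This stands as a reading of intent. It settles Month 6 against Month 12, but it does not choose among three contrasts or between Day 85 and Day 169.

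In SAP 9.3 the label comes directly after the sentence that pools the doses, so the pooled contrast might be meant. That is possible there. In section 10, however, the sentence before the label names the pooled and the by-arm analyses together.

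Imaging is secondary in a pilot of about 21 participants, and the SAP openly makes no adjustment. This stands, and it is why the error rates above describe how the results can be read and are not a breach of confirmatory error control.

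A reader might infer more than the documents support:
- *That every visit and region is co-primary.* The Month 12 analysis is outside the label. Single regions are called exploratory, only the composite has a primary model, and Appendix 2 tabulates composite and exploratory regions separately.
- *That the 68% power belongs to something other than the primary analysis.* It belongs to one component of it.
- *That only one test was powered.* A one-sample test was powered too. The pooled contrast is the only powered between-group comparison.
- *That results could be withheld.* Appendix 2 commits to tables of the pooled and by-arm results for composite and exploratory regions. The remaining risk is which result is emphasised.

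**Conclusion.** The point holds for contrast and visit. Neither document names the one comparison that leads for the primary imaging endpoint, and the wording of SAP 10 also pulls the exploratory regions under the primary label, against the direction of section 10.1.

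For composite DVR alone, the six results carry roughly a 14-18% chance of at least one nominally significant finding under no effect, against 5% for one named test. The by-arm contrasts have about 55% one-sided power, against about 68% for the pooled contrast. The power figures rest on independent scan errors; the error rates rest on the assumed correlations and on t tests in place of the mixed model.

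Sidedness is also open: the power is one-tailed, while SAP 9.3 reports two-sided intervals, and on a two-sided test the pooled contrast has about 54% power.

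No confirmatory claim depends on this, so it is a cheap improvement to the plan and not a flaw that invalidates the study.

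**What to change.** - **SAP 10:** name composite DVR, pooled CT1812 versus placebo, at Month 6 (Day 169), as the single primary imaging comparison, and state whether it is tested one-sided or two-sided. The pooled contrast is the one already powered. Day 169 is a reviewer's choice, since the power text names no visit; it matches the end of the primary treatment period.
- **SAP 9.3:** name the same contrast at Month 6 for ADAS-Cog11, which SAP 5.5 already calls the primary cognitive endpoint.
- **Both sections:** label by-arm, earlier-visit, regional and Month 12 results supportive or exploratory, with nominal p-values.

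No alpha adjustment and no change to sample size, data collection or planned tables is needed. The cost is a few sentences in the SAP. The one downside is that by-arm and earlier-visit results can no longer be called primary.

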10.3. Volumetric MRI

A composite region of AD affected brain regions will be determined, including: prefrontal, lateral temporal, posterior cingulate/precuneus, anterior cingulate, lateral parietal, medial temporal, and lateral occipital regions. An additional cerebral cortex region will also be analyzed.

Individual exploratory regions include:

- Hippocampus

- Entorhinal cortex
- Parahippocampal corte
- Amygdala
- Fusiform gyrus
- Lingual gyrus
- Inferior/middle temporal cortex
- Anterior cingulu
- Posterior cingulum
- Precuneus
- Prefrontal cortex
- Superior temporal cortex
- Lateral parietal cortex
- Lateral occipital cortex
- Pericentral cortex
- Medial occipital cortex
- Lateral ventricles

10.4. Intrinsic Connectivity Contrast (ICC)

For resting state functional MRI, the outcome will be ICC. With this approach a map of the total connectivity of each voxel to all other voxels is computed. For ICC, a composite region of AD affected brain regions will be determined, including: prefrontal, lateral temporal, posterior cingulate/precuneus, anterior cingulate, lateral parietal, medial temporal, and lateral occipital regions.

Individual exploratory regions include:

- Hippocampus
- Entorhinal cortex
- Parahippocampal cortex
- Amygdala
- Fusiform gyrus
- Lingual gyrus
- Inferior/middle temporal cortex
- Anterior cingulum
- Posterior cingulum
- Precuneus
- Prefrontal cortex
- Superior temporal cortex
- Lateral parietal cortex
- Lateral occipital cortex
- Pericentral cortex
- Medial occipital cortex

11. PHARMACOKINETIC/PHARMACODYNAMIC DATA

11.1. Pharmacokinetic Sample Collection

Blood samples for plasma concentration of CT1812 will be collected at:

- Baseline V2 (Study Day 1)
- V3 (Study Day 15)
- V4 (Study Day 29)
- V5 (Study Day 43)
- V6 (Study Day 64)
- V7 (Study Day 85)
- V8 (Study Day 106)
- V9 (Study Day 127)
- V10 (Study Day 148)
- Final/Early Discontinuation V11 (Study Day 169) (for subjects participating in the Primary Study Only)
- V13 (Study Day 253) (for subjects participating in the Extension Study)
- Final/Early Discontinuation V15 (Study Day 337) (for subjects participating in the Extension Study)

CSF samples for concentration of CT1812 will be collected at:

- V1 (Study Day -60 to -1)/Step 4
- Final/Early Discontinuation V11 (Study Day 169) (for subjects participating in the Primary Study Only)
- V11 (Study Day 169) (for subjects participating in the Extension Study)
- Final/Early Discontinuation V15 (Study Day 337) (for subjects participating in the Extension Study)

11.2. Pharmacokinetic Concentrations

Plasma concentrations of CT1812 will be listed and plotted across collection days for each subject, and summarized with descriptive statistics by treatment group.

Plasma concentrations of CT1812 that are less than the limit of quantification (LOQ) of the assay will be designated a value of zero for the summation of concentration-time data.

Concentration data in listings will be presented to the same number of significant figures as provided by the analytical laboratory. Summary statistics will be displayed to the number of decimal places appropriate for the accuracy of the data.

Individual and summary pre-dose concentrations will be plotted across collection days with the plasma concentration axis displayed on a linear scale and on a logarithmic scale.

CSF concentrations will be listed for each subject, and summarized with descriptive statistics by dose level / treatment group. In addition, CSF and Plasma concentrations of CT1812 concentrations will be normalized on both a mg-dose and a mg/kg-dose basis to account for both dose and body weight. CT1812 CSF and plasma concentration will be time matched and the CT1812 CSF/plasma concentration ratios will be determined and summarized using descriptive statistics.

11.3. Pharmacokinetic Parameters

No pharmacokinetic parameters will be determined in this study.

11.4. Statistical Analysis of Pharmacokinetic Parameters

No pharmacokinetic parameters will be analyzed in this study.

11.5. Pharmacodynamic Endpoints

CSF samples will also be used for the evaluation of the following biomarkers associated with Alzheimer's disease:

- A β 40 monomer
- A β 42 monomer
- Tau
- phospho-tau
- neurogranin
- Synaptotagmin
- synpatosomal-associated protein-25 (SNAP25)
- NFL
- YKL-40 ELISA
- neuronal pentraxin-1
- neuronal pentraxin -2
- neuronal pentraxin receptor
- complexin-2
- syntaxin-1b
- syntaxin-7
- gamma-synuclein
- rab GDI alpha
- Phosphatidylethanolamine-binding protein 1
- AP-2 complex subunit beta
- 14-3-3 protein zeta/delta

CSF concentrations will be listed and plotted across collection days for each subject.

CSF concentrations less than the LOQ of the assay for pharmacodynamic analysis will be designated either a value of zero or of LOQ, as applicable, after clarification from the Sponsor.

11.6. Pharmacodynamic Analysis

Pharmacodynamic endpoints of CSF will be summarized by treatment and timepoint, using descriptive statistics for the original measurements as well as the change from baseline for continuous endpoints.

11.7. Statistical Analysis of Pharmacodynamic Parameters

Change from baseline in pharmacodynamic endpoints of CSF will be analysed using the MMRM or ANCOVA model described in section 9.3. The analysis will be performed for time points up to and including the 6-month time point, and 12-month time point respectively.

11.8. Changes from the Analysis Planned in the Protocol

There are no changes from the planned analysis described in the protocol.

12. DATA LISTINGS AND SUMMARY TABLES

12.1. Interim/Preliminary Data Analysis

No interim analyses are planned.

12.2. Listings and Tables for Clinical Study Report

The data listings and summary tables, and associated figures, planned to be generated from the study data are listed in Appendix 1 and Appendix 2, respectively. The numbering and titles may vary in the final presentation, depending on the amount of data to be presented.

Listings, tables and figures will be provided to the Sponsor in a form suitable for inclusion as appendices to the Clinical Study Report, in RTF or PDF format. The layout will be landscape A4 size, with a margin of 1 inch. The default font for listings and tables will be Courier New 8 pt.

In the summary tables other than those included in the main text of the report, special characters and formatting will not be used.

Data in listings will be ordered by cohort, then subject, then date/time. Screen failed subjects will be identified in the listings.

Data to be presented graphically includes: Concentration-time data for each subject, and mean concentration values at each nominal sampling time-point for plasma CT1812 concentration.

Mean values for total scores for cognitive and clinical outcomes (ADAS-Cog14, NTB, ADCS-ADL, MMSE, CDR-SB) will be presented graphically by treatment group over time.

12.3. Data Transfer to the Study Sponsor

At the conclusion of the study, Avance will provide the Sponsor with an electronic copy of the listings, tables and graphs. This may be provided by email or by upload, as determined by the Sponsor.

Details of the statistical analyses will be retained in the Avance study file for reference.

13. GENERAL CONSIDERATIONS FOR DATA MANAGEMENT AND ANALYSIS

13.1. Analysis Packages

SAS 9.4 or higher (SAS Institute Inc., Cary, NC, USA) will be used for generating data listings and summary tables and associated figures, and for performing statistical analysis.

13.2. Electronic Data Management

All listings, tables and figures for inclusion in the appendices of the clinical study report will be generated using SAS programs.

A copy of final listings, tables and figures will be retained in the Avance internal study file. A tracking log will be maintained detailing the date and initials of the staff member responsible for generating each listing, table or figure, and the staff member conducting the quality control review. Any erroneous results identified during subsequent checking process will be corrected by update of the SAS program, and the document recreated and then re-checked. To ensure an accurate data trail is maintained, corrections to electronic documents will be included on the tracking log, detailing the correction along with the date of the new version as well as the initials of the staff member responsible for the change and the verifying staff member. If statistical analysis is repeated with a modified data set, the new data produced will be saved as a new file.

